4 METHODOLOGY

4.1 Study Design

This is a double arm, single-blinded randomized trial evaluating the use of botulinum toxin injection as a pyloric drainage procedure. The study is expected to accrue patients over 4 years. The study schema is depicted below in **Figure 1**.

Figure 1 Study Schema

All patients considered for minimally invasive esophagectomy in our surgery practice will receive routine work-up and multidisciplinary evaluation and care for esophageal carcinoma, which may include neoadjuvant therapy. Patients will be given a patient consent form that will inform them of the possible risks and benefits of this study. Patients will undergo the standard of care preoperative work-up, during which it will be determined if they meet the inclusion and exclusion criteria summarized in **Section 5.1** and **Section 5.2** prior to enrollment in the study. If criteria are met, patients will be randomized by the study coordinator, per methods determined by the statistician. The randomization allocation will be shared with the surgical team from the study coordinator to the surgeon prior to the surgery and discussed during the surgical time-out. The next 50 patients who meet the study criteria will be randomized to either the intrapyloric botulinum injection arm or the non-botulinum treatment arm. All participants will sign a surgical consent prior to minimally invasive esophagectomy.

All patients will undergo routine minimally invasive esophagectomy. If randomized to the botulinum arm, patients will undergo the standard minimally invasive esophagectomy performed at RPCI, including intra-pyloric botulinum injection. If randomized to the no botulinum arm, patients will undergo the standard minimally invasive esophagectomy performed at RPCI **excluding** the pyloric drainage procedure with botulinum injection. The patient and radiologist

will be blinded to the treatment arm. The surgeon, due to the nature of the intervention, will not be blinded to the treatment arm.

The standard of care for minimally invasive esophagectomy at RPCI is outlined in the following postoperative pathway. **All patients follow this pathway unless clinical status dictates otherwise:**

- Patients leave the operating room with a nasogastric tube (NGT) tip at or beneath the esophago-gastric anastomosis, and a feeding jejunal-tube (j-tube).

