As a participant in this study the patient will undergo a ***nuclear medicine emptying study*** to assess for conduit function. This study will be obtained within the window of Postoperative Visit #2 (± 14 days). *Prior to the nuclear medicine emptying study*, the patient must be fasting for at least 6 hours; including oral intake and any supplemental j-tube feeds. The fasting glucose should be measured and less than 275 mg/dL. Patients should be off all narcotic pain medications for the 48 hours prior to the nuclear medicine emptying study.

- 120 mL of liquid egg white product (Egg Beaters) will be radiolabeled with 1 mCi of Tc99m, cooked and then scrambled. The patient will be instructed to ingest the meal within 10 minutes. Images will be obtained every 15 minutes for up to four hours. If the patient vomits part of the meal at any time during the test, it will be recorded on the study report.
- During the study, for the time between the images, the patients may be sitting, standing, or walking, but should remain in close proximity to the nuclear medicine facility. Patients will be monitored for any symptoms of delayed gastric emptying during this time. Participants will answer a questionnaire to assess for gastrointestinal symptoms during the nuclear medicine study (See **Appendix C**).

A single nuclear radiologist, who is blinded to the randomization group, will assess gastric emptying on the nuclear emptying study. There is no standardized method for reporting conduit emptying by this method. Two published studies on this topic have used time to 50% gastric emptying as an endpoint (8), and categorized 50% gastric emptying into ranges, with >180 minutes categorized as “delayed,” within 180 minutes as “intermediate,” and immediate emptying as “rapid” (12). We will measure time to 50% gastric emptying in all patients, and categorize similar to the above description, as follows:

Table 1 50% Gastric Emptying Times and Definitions:

Definition	50% Emptying Time
Rapid	Immediate emptying, no radiotracer seen on first image obtained at 15 minutes
Intermediate	$<$ or $=$ 150 minutes
Delayed	$>$ 150 minutes

This time modification is based on the current guidelines and normal limits for gastric retention assessed by nuclear scanning (13). The report will also include the percentage of tracer retained the following times after meal ingestion: 1, 2, 3, and 4 hours.

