To ensure the radiologist interpreting the nuclear medicine and gastrografin studies/CT esophagram remains blinded, the radiologist should not open the “operative note” documents in

the electronic medical record. During study interpretation, if the radiologist requires clarification regarding the operative procedure, he should contact the operating surgeons directly. The randomization group will not be listed in any other part of the electronic medical record.

Primary Endpoint

- Postoperative delayed gastric emptying assessed radiographically as “severe” by nuclear medicine emptying study compared to “intermediate,” and “rapid” emptying. “Severe” delayed gastric emptying will be defined as scoring of “delayed” on nuclear emptying study. Patients assessed as “intermediate” or “rapid” on nuclear medicine emptying study will be considered to have normal conduit function.

Secondary Endpoints

- Postoperative delayed gastric emptying assessed radiographically by gastrografin swallow /CT esophagram.
- Postoperative delayed gastric emptying assessed clinically by the following:
 1. Quality of life score assessed by EORTC QLQ-C30 OES18.
 2. Pulmonary events directly related to delayed gastric emptying, as assessed by the operating surgeon. Pulmonary events include pneumonia, acute aspiration, and respiratory failure requiring intubation.
 3. Gastrointestinal and nutritional status: Requirement of NGT past Postoperative Day #7, or need to reinsert NGT, witnessed nausea, vomiting, or regurgitation directly related to delayed gastric emptying. This does not include postoperative ileus. Tolerance of full liquid diet at hospital discharge and meeting nutritional goals of time to resumption of 50% caloric needs orally by Postoperative Day #7, 75% caloric needs orally by Postoperative Day #21, and 100% caloric needs orally by Postoperative Day #35.
 - “Moderate” delayed gastric emptying will be defined as clinical symptoms requiring medical therapy.
 - “Severe” delayed gastric emptying will be defined as clinical symptoms requiring secondary procedure.
 4. Hospital length of stay attributed to delayed gastric emptying.
 5. Number of secondary procedures within 90 days due to delayed gastric emptying. Secondary procedures include endoscopic or operative procedures for delayed gastric emptying.
 - Requirement of secondary procedure will be graded as “Severe” delayed gastric emptying

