9.4 Primary and Secondary Analyses

Primary Analysis: A recent study demonstrated that patients who received Botox had a delayed gastric emptying rate of approximately 30% as compared to a complication rate in historical controls of 70% in patients that did not receive botulinum toxin injection (7). A retrospective review of patients undergoing minimally invasive esophagectomy at Roswell Park Cancer Institute indicates that the rate of postoperative delayed gastric emptying is even lower, however, this rate is based on very stringent criteria for delayed gastric emptying- requirement of a secondary procedure. Therefore, the primary objective is to determine if intra-pyloric botulinum toxin injection during a minimally invasive esophagectomy decreases postoperative occurrence of delayed gastric emptying. The primary outcome is delayed gastric emptying (assessed radiographically by nuclear medicine emptying study) which is treated as a dichotomous variable.

Patients will be stratified by receipt of neoadjuvant chemoradiotherapy, smoking status, and diabetes; and randomized in a 1:1 to the botulinum and non-botulinum treatment arms. The primary objective will be assessed using the intent-to-treat principle and a one-sided Cochran-Mantel-Haenszel (CMH) s test about the following hypotheses:

$$\begin{aligned} H_0: \theta &\geq 1, \\ H_A: \theta &< 1 \end{aligned}$$

where θ is the common odds ratio (COR) for the odds of delayed gastric emptying rates for the botulinum versus non-botulinum treatment arms. A one-sided test is performed as the rate of delayed gastric emptying is expected to decrease in the botulinum arm over the non-botulinum arm; that is, we expect $\theta < 1$.

The analysis will proceed in two stages using an O'Brien-Fleming alpha spending function. An interim analysis will be conducted after $n_1=30$ patients have completed treatment and the final analysis will be conducted after $n=50$ patients have completed treatment. The following decision rules will be utilized at each analysis:

Analysis	Decision Rule
Interim	
• If $p\text{-value} \leq 0.011396$, then reject H_0 and stop due to superiority.• If $\hat{\theta} > 1$, then stop due to inferiority.• Otherwise enroll $n_2=20$ patients.
Final	
• Reject H_0 if $p\text{-value} \leq 0.046533$

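### Section 4.1 allows the blinded reader of the primary endpoint to ask the unblinded operating surgeons about the operation, with no limit on, or record of, what is said

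*Combined protocol and SAP*

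**What the plan says.** Section 4.1 gives the primary reading to one person: "A single nuclear radiologist, who is blinded to the randomization group, will assess gastric emptying on the nuclear emptying study". Section 9.4 makes that reading the primary outcome: "The primary outcome is delayed gastric emptying (assessed radiographically by nuclear medicine emptying study) which is treated as a dichotomous variable". No second reader or adjudication is described.

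The surgeon knows the arm. Section 4.1 states: "The randomization allocation will be shared with the surgical team from the study coordinator to the surgeon prior to the surgery", and then: "The surgeon, due to the nature of the intervention, will not be blinded to the treatment arm".

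A paragraph in Section 4.1 sets out how the reader of the nuclear and gastrografin/CT studies is to stay blinded. It has three parts:

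- The record: "the radiologist should not open the “operative note” documents in" the electronic medical record.
- The allocation: "The randomization group will not be listed in any other part of the electronic medical record".
- Queries during interpretation: "if the radiologist requires clarification regarding the operative procedure, he should contact the operating surgeons directly".

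**The concern.** The operative note is closed to the radiologist because it would show whether the pylorus was injected. The third part of the same paragraph then lets him raise the same subject with people who know the answer, while he is still reading the scan. The safeguard and its exception pull against each other.

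The blinded scan reading carries much of this trial's credibility. The surgeon is unblinded, and Section 4.1 also has the operating surgeon judge whether pulmonary events are related to delayed emptying. If the scan reader learns the arm before fixing the category, the primary comparison loses protection for that patient. Nothing in the plan would show that it had happened.

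**Working it through.** No figure in the plan measures this point, so the main check is to read the provisions together.

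**1. What the contact knows.** The operating surgeons receive the allocation before surgery (Sections 4.1 and 6.3). They are not alone in this: the study coordinator randomizes and relays the allocation (Sections 4.1, 6.3 and 9.2), and it is discussed at the surgical time-out.

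**2. What the topic can reveal.** Under Section 6.3 both arms have the same operation, with or without the pyloric injection. A full account of the procedure therefore identifies the arm. An answer confined to conduit or anastomosis anatomy does not.

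**3. What limits the exchange.** I looked for a rule on what the surgeon may say, a scripted or blinded intermediary, a log of contacts, and a rule for a reading made after disclosure. The plan contains none of these. The only constraint is the paragraph's stated aim of keeping the radiologist blinded.

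**4. How much judgement the reading leaves.** Table 1 in Section 4.1 classes a scan as delayed when the time to 50% emptying exceeds 150 minutes. Images are taken every 15 minutes, so the cut falls at the tenth interval (150/15 = 10). This is a measured quantity with a fixed threshold. Section 4.1 also says, however, that no standardized method exists for reporting conduit emptying. It gives no rule for drawing the conduit region or for interpolating between images, and it asks only that vomiting of part of the meal be recorded. Scans near the cut still need judgement.

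**5. Illustration of scale, on assumed misreading rates.** Suppose the true rate is 0.70 in both arms (the null case of Section 9.1). A share f of delayed Botox scans is read as not delayed, and the same share f of non-delayed control scans is read as delayed. The rates as read are then:

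- Botox: 0.70 × (1 − f)
- Control: 0.70 + 0.30 × f

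With 25 patients per arm, the expected number of misread scans is 25 × 0.70 × f + 25 × 0.30 × f = 25f.

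The two-stage design was simulated with 30 then 50 patients, bounds 0.011396 and 0.046533, and a stop at the interim if the odds ratio exceeds 1. No continuity correction was used. The stratified version used eight strata with assumed factor prevalences of 0.5, 0.5 and 0.2.

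| f | Botox rate as read | Control rate as read | Expected misread scans of 50 | Chance of declaring Botox superior (stratified to unstratified) |
|---|---|---|---|---|
| 0 | 0.700 | 0.700 | 0 | 5.0% to 5.3% |
| 5% | 0.665 | 0.715 | 1.25 | 9.9% to 10.9% |
| 10% | 0.630 | 0.730 | 2.5 | 17.7% to 19.6% |
| 20% | 0.560 | 0.760 | 5 | 42.1% to 45.8% |

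Section 9.1 gives 4.3% for the first row. The unstratified simulation with continuity correction gives 2.4%, so the plan's figure lies between the variants. The plan does not state which strata or test variant its simulation used.

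The documents give no basis for choosing f. It is the product of three shares: scans queried, queries that disclose the arm, and readings then shifted. It therefore cannot exceed the share of those scans that are queried. The direction is also open. Sections 1.1 and 1.2 hypothesize that the injection does not work, whereas Section 9.4 expects an odds ratio below 1. Bias against Botox would cost power instead.

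**The case against.** The strongest reply is that the paragraph exists to protect blinding and should be read that way. Contact is conditional and replaces opening a note that would show the injection. A surgeon working under the same protocol can answer an anatomy question without naming the arm. The endpoint is a measured time with a fixed cut, which leaves less room for bias than a subjective score.

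Most of this stands, and it limits the weight of the point. It does not remove it. A stated purpose is not a rule on what may be disclosed, no record would show whether the purpose was kept, and scans near 150 minutes still involve choices that the plan does not fix.

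Three stronger readings are tempting and go beyond the documents:

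- A reader might infer that the blinding fails. The text shows only a route that may never be used.
- A reader might infer that the surgeon alone knows the arm. The coordinator and the surgical team know it too, which matters for the choice of remedy.
- A reader might argue that one changed scan could decide a 50-patient trial. Any binary trial of this size has results at the rejection boundary, and that says nothing about how often contact, disclosure or misreading would occur.

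**Conclusion.** The point holds as a gap in procedure. The plan bars one source of operative detail to keep the reader blinded and opens another through unblinded colleagues, without limit or log. It affects the single reader of the primary endpoint. Because the paragraph names both kinds of study, it also affects the gastrografin/CT reading, whether or not the same radiologist does both.

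The size of any bias cannot be derived from the documents. The table shows what follows if misreading is assumed, systematic and in Botox's favour; it does not predict that this will happen. The conclusion rests on the text alone: an unblinded contact, arms that differ by an operative step, no restriction on content, and a reading that keeps some judgement. The change is worth making because the route is avoidable at very little cost.

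**What to change.** Replace the contact sentence in Section 4.1, for endpoint scoring only, with a rule along these lines:

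- The radiologist records the time to 50% emptying (for the swallow or CT study, the emptying score) and the category before any query.
- Questions are put and answered in writing, from a standard summary or form limited to conduit and anastomosis anatomy. The form omits the pylorus, the injection and the arm.
- The coordinator may pass the form on, but also knows the allocation. The protection comes from the restricted content, not from the intermediary.
- Every contact is logged, as is any accidental unblinding. If an answer changes a reading, the change is logged and the original kept. The plan should state in advance which of the two enters the primary analysis.
- Clinical reading of the swallow or CT study for anastomotic leak stays outside this rule, so that communication about it is not slowed.

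The cost is one paragraph, a one-page form and slightly slower replies to scoring queries. Sample size, analysis method and clinical care do not change.

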4.2 Target Accrual and Study Duration

A maximum of 50 evaluable patients at RPCI will be enrolled. Accrual is expected to take up to 6 years.

This target accrual and study duration is highly feasible based off the high volume of patients with esophageal carcinoma undergoing minimally invasive esophagectomy at RPCI. An interim analysis will occur after 30 patients have been enrolled.

Study participants will be followed for data collection for 90 days (routine post-esophagectomy follow-up care and surveillance, per standard of care).

A patient will be replaced on study if the following deviations from the original surgical plan occur:

- the surgical procedure is converted to open technique or,
- a cervical anastomosis is performed or,
- a patient does not complete the postoperative evaluation through the nuclear medicine emptying study obtained within \pm 14 days of post-operative visit #2.

5 PARTICIPANT SELECTION

5.1 Inclusion Criteria

To be included in this study, participants must meet the following criteria:

1. Esophageal carcinoma, undergoing minimally invasive esophagectomy with intrathoracic anastomosis.
2. Age \geq 18 years of age.
3. Have an ECOG Performance Status of \leq 2. Refer to **Appendix A**.
4. Participant must understand the investigational nature of this study and sign an Independent Ethics Committee/Institutional Review Board approved written informed consent form prior to receiving any study related procedure.

5.2 Exclusion Criteria

Participants will be excluded from this study for the following:

1. Patients who have a history of gastrointestinal dysmotility or functional gastroparesis, including diabetic gastroparesis, central and peripheral nervous system disorders, renal failure, medication side effects, including chronic dependence of promotility agents, anticholinergic antispasmodic agents, or chronic narcotic use over 2 years due to non-cancer causes. Refer to **Appendix B** for a list of pharmacologic agents.
2. Patients who have a history of previous gastric or duodenal surgery.
3. Patients who have a history of duodenal ulcer or duodenal fibrosis.
4. Uncontrolled intercurrent illness including, but not limited to, ongoing or active infection, symptomatic congestive heart failure, unstable angina pectoris, cardiac arrhythmia, or psychiatric illness/social situations that would limit compliance with study requirements.
5. Allergy to botulinum toxin, and or egg.
6. Pregnant or nursing female participants.

7. Unwilling or unable to follow protocol requirements.
8. Any condition which in the Investigator's opinion deems the participant an unsuitable candidate for study participation.

5.3 Inclusion of Women and Minorities

Both men and women and members of all races and ethnic groups are eligible for this study.

6 STUDY PROCEDURES

The study-specific assessments are detailed in this section and outlined in **Table 2** (Schedule of Procedures and Observations). Standard preoperative screening assessment and multidisciplinary evaluation must be performed up to 6 weeks prior to minimally invasive esophagectomy. The nuclear medicine emptying study may occur within the window of Postoperative Visit #2 (\pm 14 days) unless contraindicated per physician's discretion. Unless otherwise defined in the written protocol text, all procedures/assessments will be conducted in accordance with RPCI Clinical Research Services Standard Operating Procedures. All procedures and evaluations listed are our post-esophagectomy standard of care at RPCI except for Nuclear Medicine Emptying Study, EORTC QLQ OES18 Questionnaire, and *routine* postoperative outpatient assessment by our dietitian.

6.1 Participant Randomization and Registration

Eligibility of each participant will be established prior to randomization.

Informed consent **MUST** be completed prior to receiving any study related procedures.

Participants will be randomized in a 1:1 fashion to the botulinum and non-botulinum treatment arms using a permuted block design. The randomization list will be developed by the Department of Biostatistics and Bioinformatics, and randomization procedure as outlined in **Section 9.2**.

6.2 Baseline Evaluations

Preoperative workup and multimodality therapy for esophageal cancer as standard of care at RPCI, based upon the NCCN guidelines for esophageal cancer. Standard presurgical assessment with full medical history and physical examination, laboratory tests, cross-sectional imaging and cardiopulmonary assessment as determined by the operating surgeon or the Preoperative Anesthesia Clinic based upon RPCI established guidelines.

The following will be performed prior to the participant's scheduled minimally invasive esophagectomy and will be confirmed before surgery:

- Informed consent for study. Must be completed prior to receiving any study-related procedures.
- Medical history with preexisting conditions, including all neoadjuvant therapy related to esophageal carcinoma, smoking status and, diabetes.

- Physical examination, including vital signs (i.e., temperature, heart rate, respiratory rate, blood pressure), body weight and height; with emphasis on the neck, thoracic, and abdominal cavities.
- Multidisciplinary evaluation and neoadjuvant therapy if indicated for esophageal carcinoma. Multidisciplinary evaluation will be documented in the outpatient preoperative office visit note.
- Pregnancy test (urine) in females of childbearing potential. The standard operating procedure for all females of childbearing potential in the Ambulatory Surgical Center (ASC) pre-op holding area is to obtain a urine HCG. This study protocol does not deviate from the standard operating procedure of the ASC/pre-op holding area at RPCI. If the pregnancy test is positive, the patient is excluded from the study.
- Nutritional status assessment by a dietitian, as clinically indicated.

The following will be performed if indicated by the anesthesia pre-op assessment (standard operating procedure for the pre-op clinic at RPCI). These tests are not strictly required to support eligibility for this study, but if indicated and performed, may exclude the patient from receiving a general anesthetic and thereby excluding the patient from this study.

- Hematology: CBC with automated differentials (WBC, RBC, HGB, HCT, platelet, MCV, MCH, MCHC, % neutrophils, absolute neutrophils, % monocytes, absolute monocytes, % eosinophils, absolute eosinophils, % basophils, absolute basophils, % lymphocyte, absolute lymphocyte, platelet confirmation (as clinically indicated), and differential confirmation (as clinically indicated).
- Chemistry (i.e., complete metabolic panel (CMP)): chloride, CO₂, potassium, sodium, BUN, glucose, calcium, creatinine, total protein, albumin, total bilirubin, alkaline phosphatase, AST, ALT, A/G ratio, BUN/creatinine ratio, osmol (Calc), anion gap).
- 12-lead electrocardiogram, chest x-ray, pulmonary function tests, and cardiac stress test, if indicated.

